8.1 Sample size

51 patients (30 patients with carcinoid and 21 patients with pNET).

8.2 Endpoints to be followed

Efficacy Endpoints

- Tumor response rate using RECIST (Primary endpoint);
- OS, determined from the time of drug administration to death from any cause (Secondary endpoint);
- PFS, determined as the time from administration of the initial dose of ibrutinib until objective tumor progression using RECIST, or death (Secondary endpoint);
- Duration of response, defined as time from first observation of an objective response which is subsequently confirmed, to first disease progression or death due to any cause (Secondary endpoint);
- Changes in health-related quality of life, as assessed by EORTC questionnaires EORTC QLQ-C30 and QLQ GI.NET21 (see section 11).

Safety Endpoint

Safety assessments will consist of monitoring and recording all adverse events and serious adverse events, the regular monitoring of hematology and blood chemistry parameters and regular physical examinations. Adverse events will be evaluated continuously throughout the study. Safety and tolerability will be assessed according to the NIH/NCI Common Terminology Criteria for Adverse Events version 4 (CTCAE v4) available at: http://ctep.cancer.gov/protocolDevelopment/electronic_applications/ctc.htm. All adverse events will be documented on the adverse event CRF.

Exploratory Analyses (refer to Section 6.3)

As part of this study, we will explore the correlation between early biochemical response and response rates or PFS. Early biochemical responders will be defined as patients with elevated chromogranin A (CgA) who experience a major reduction (>50%) or normalization of their CgA between their baseline (pretreatment) measurement and their follow-up assessment 3 months later.

We also plan to undertake an exploratory analysis of blood- and tissue-based markers that may correlate with the clinical outcomes observed in the study. Exploratory markers will include the measurement of serum Tryptase- β 2 and the determination of the presence and activation of mast cells in the tumor tissue samples.

Archival pathology specimens will be reviewed at the study institution (Moffitt Cancer Center) for determination of mitotic rate (number of mitoses per 10 high-powered fields) and Ki-67 index.

This study is not sufficiently powered to establish definitive outcome for the correlative endpoints. These results will be considered hypothesis generating and any comparison with a significant alpha <0.05 will be deemed of sufficient interest to warrant further evaluation.

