1.4 Study rationale

It is becoming increasingly clear that the microenvironment has a crucial role in the progression of both hematological and solid tumors. In particular, preclinical data suggests that mast cells are recruited within NETs where they remodel the stroma and stimulate angiogenesis, driving macroscopic tumor expansion¹⁶. Inhibitors of mast cell degranulation have been shown to block this process, driving tumor shrinkage, at least in mouse models²². Ibrutinib can affect mast cell degranulation, acting downstream the high affinity IgE receptor FcεRI¹⁹. Given its favorable risk/benefit ratio for investigation in NETs, we plan to test the hypothesis whether ibrutinib can cause tumor regression in both carcinoid tumors and pNETs.

2. Study objectives

The primary purpose of the study is to determine the objective response rate to ibrutinib therapy in patients with advanced (unresectable or metastatic) low to intermediate grade carcinoid tumors or pNETs.

Secondary objectives are:

- to investigate the progression-free survival (PFS) and overall survival (OS) associated with ibrutinib in patients with advanced carcinoid tumors or pNETs;
- to evaluate the duration of response of carcinoid or pNET patients receiving ibrutinib;
- to assess changes in tumor markers and changes in quality of life (QOL) in NET patients administered with ibrutinib;
- to determine the safety and tolerability of ibrutinib in this patient population.

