3.3 Exploratory endpoint

1. To determine whether the presence and activation of mast cells in the tumor tissue sample predicts for response;
2. To determine whether changes in serum Tryptase-β2 correlate with response.

4. Investigational plan

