6.3.1 Blood-based biomarkers

Blood will be collected every three months. Serum measurement of Tryptase- β 2 will be performed by ELISA in the Translational Research Core of the Moffitt Cancer Center.

6.3.2 Tissue-based biomarkers:

If available, archival tissue containing a tumor block (preferred) or 10 unstained slides (3-5 micron thick) from patient's primary or metastatic neuroendocrine tumor should be sent to Moffitt Cancer Center for correlative immunohistochemical studies. Specimens should be placed in a secure, airtight container, labeled with the patient name and study number.

Site should contact Moffitt Cancer Center at [contact] with expected delivery date.

Shipping address:

Attention [name]
Anatomic Pathology Dept.
H. Lee Moffitt Cancer Center
[name]
[name]

Immunohistochemistry (IHC) will be used to evaluate the expression of c-kit, tryptase and chymase as markers for mast cell presence and activation, respectively. Sections of 3-4 microns in thickness will be cut from the selected formalin-fixed paraffin embedded tissue and subjected to IHC staining protocol using the Dakocytomation Autostainer (DakoCytomation, Carpinteria, Calif). Microwave antigen retrieval with IHC Select EDTA buffer, pH 7.5, will be utilized. Primary antibodies with cross-reactivity against the human subtypes of the above mentioned targets will be diluted and incubated for 60 minutes at room temperature. Using a semiquantitative scoring system, the intensity of IHC staining for c-kit, chymase and tryptase will be scored as either 0 (negative), 1+ (mild positive staining), 2+ (moderate positive) and 3+ (strong positive staining). The correlation between staining patterns and clinical outcomes (response rate or PFS) will be analyzed in a descriptive fashion.

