Target lesions: all measurable lesions up to a maximum of two lesions per organ and five lesions in total, representative of all involved organs, should be identified as target lesions and will be recorded and measured at baseline. Target lesions should be selected on the basis of their size (lesions with the longest diameter) and their suitability for accurate repetitive measurements (either by imaging techniques or clinically). A sum of the diameters (longest for non-nodal lesions, short axis for nodal lesions) for all target lesions will be calculated and reported as the baseline sum diameters. The baseline sum diameters will be used as reference to further characterize the objective tumor response of the measurable dimension of the disease. If lymph nodes are to be included in the sum, only the short axis will contribute.

Non-target lesions: All lesions (or sites of disease) not identified as target lesions, including pathological lymph nodes and all non-measurable lesions, should be identified as non-target lesions and be recorded at baseline. Measurements of these lesions are not required and they should be followed as ‘present’, ‘absent’ or in rare cases, ‘unequivocal progression’.

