7.1.1 Evaluation of target lesions

Complete response (CR): complete disappearance of all target lesions, confirmed by repeat assessments at no less than 4 weeks after the criteria for response are first met. Any pathological lymph nodes (whether target or non-target) must have reduction in short axis to <10 mm

Partial response (PR): at least a 30% decrease in the sum of diameters of target lesions, taking as reference the baseline sum longest diameter. This must be confirmed by repeat assessment at no less than 4 weeks after the criteria for response are first met.

Progressive disease (PD): at least a 20% increase in the sum of diameters of target lesions, taking as reference the smallest sum on study (this may include the baseline sum). The sum must also demonstrate an absolute increase of at least 5 mm.

Stable Disease (SD): neither sufficient decrease to qualify for partial response nor sufficient increase to qualify for progressive disease.

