8.3 Sample-size Calculation

This will be a standard, phase II study, in which two cohorts of patients (carcinoid and pNET) consisting of 30 patients with carcinoid tumors and 21 patients with pNET each will be enrolled.

We have designed the study to test the null hypothesis that ibrutinib has a response rate of 5% or less in this disease. The sample size calculation has been based on the assumption that a true response of greater than 18% (comparable with that seen with agents such as sunitinib in pNET¹³ or bevacizumab in carcinoid tumors³¹) would generate interest in a larger randomized study. Taking into account both study feasibility given these relatively rare tumor and the relatively small difference in H1 and H0, with 30 patients in the carcinoid cohort we will be able to test the hypothesis that the true response is 18% versus 5% with a power of 80% and a type 1 error of 6%, while with 21 patients in the pNET cohort we will be able to test the hypothesis that the true response is 20% versus 5% with a power of 80% and a type 1 error of 8%. Patients will be accrued to the protocol according to a Simon's two-stage minimax design. In the carcinoid cohort, 15 subjects will be enrolled into stage-1. If 1 or more response is observed, then another 15 subjects will be enrolled into stage-2. At the completion of the study, if 4 or more responses out of N=30 are observed, significance at 6% is reached. Under this design, and if the true response rate is ≥18%, then the probability of observing ≥1 response in stage-1 is ≥95%. In the pNET cohort, 12 subjects will be enrolled into stage-1. If 1 or more response is observed, another 9 subjects will be enrolled into stage-2. At the completion of the study, if 3 or more responses out of N=21 are observed, significance at 8% is reached. Under this model, and if the true response rate is ≥20%, the probability of observing ≥1 response in stage-1 is 93%. In both cohorts, at least 1 patient must respond in the first stage to proceed to the second stage. At any point when it is realized that this cannot happen, the study will be stopped in the relative cohort, where the therapy will be considered ineffective.

Kaplan-Meier survival analysis will be performed to evaluate OS, PFS and duration of response.

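### The exploratory marker analyses use confirmed RECIST response as their only named shrinkage outcome; adding percentage change in the target-lesion sum would be a cheap, low-priority improvement

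*Combined protocol and SAP*

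**What the plan says.** Section 3.3 lists two exploratory aims: "To determine whether the presence and activation of mast cells in the tumor tissue sample predicts for response" and "To determine whether changes in serum Tryptase-β2 correlate with response". For tissue, section 6.3.2 adds PFS and sets the level of ambition: "The correlation between staining patterns and clinical outcomes (response rate or PFS) will be analyzed in a descriptive fashion". For CgA, section 8.2 states that "we will explore the correlation between early biochemical response and response rates or PFS". For tissue and tryptase, section 8.2 refers only in open terms to the clinical outcomes seen in the trial. It also says that the correlative work is underpowered and hypothesis generating, and it flags any comparison below 0.05 for further study.

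Response here is a confirmed category. Section 7.1.1 requires "at least a 30% decrease in the sum of diameters of target lesions" for a partial response, and sections 7.1.1 and 7.3 require confirmation at least 4 weeks later. The measurements beneath that category are collected throughout:

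- Measurable disease is an entry criterion (4.4.1).
- The baseline sum is calculated and reported: "The baseline sum diameters will be used as reference to further characterize the objective tumor response of the measurable dimension of the disease" (7.1).
- Lesions are re-measured at each evaluation (7.1.2).
- Scans are repeated every 12 weeks (Table 6-5, footnote h).

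Percentage change in the sum is not named as an outcome of any analysis. The hypothesis in section 1.4 is about regression: "we plan to test the hypothesis whether ibrutinib can cause tumor regression in both carcinoid tumors and pNETs".

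**The concern.** The tissue and tryptase analyses are the trial's only look at the mast-cell mechanism that motivates it. Their shrinkage outcome is a rare yes/no event in two small cohorts. If shrinkage is graded, a patient whose lesions shrink by 25% and one whose lesions grow by 15% are both non-responders, and the difference between them is lost. That loss is largest when the drug is weak, which is when a mechanistic signal would be hardest to see. In the extreme case no patient responds and a marker cannot be compared with response at all, although every treated patient had measurable lesions. What is at stake is the yield of exploratory work, not the trial's primary conclusion.

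**Working it through.** **Inputs (section 8.3).** Carcinoid: 15 patients in stage 1, 15 more in stage 2, at least 4 responses of 30 to succeed, 5% versus 18%. pNET: 12, then 9 more, at least 3 of 21, 5% versus 20%. The continuation rule is "In both cohorts, at least 1 patient must respond in the first stage to proceed to the second stage". The 10% rate is an added intermediate scenario, not a figure in the plan.

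**Reproducing the plan.** Exact two-stage binomials give:

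- Carcinoid: type 1 error 5.82% (stated 6%) and power 80.0% (stated 80%).
- pNET: type 1 error 8.04% (stated 8%) and power 80.3% (stated 80%).
- Chance of at least one stage-1 response at the design rates: 94.9% and 93.1% (stated 95% and 93%).

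The design figures reproduce at the stated rounding.

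**Expected responders.** For each cohort, with S = (1−p)^n1 the chance of stopping, the expected number is p × [n1 + (1−S) × n2].

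- At 5%: S = 0.95^15 = 0.463 and 0.95^12 = 0.540. Carcinoid 0.05 × (15 + 0.537×15) = 1.15; pNET 0.05 × (12 + 0.460×9) = 0.81; total 1.96.
- At 10%: S = 0.206 and 0.282. 2.69 + 1.85 = 4.54.
- At 18%/20%: S = 0.051 and 0.069. 5.26 + 4.08 = 9.34.

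With no stopping rule the totals would be 51×0.05 = 2.55, 51×0.10 = 5.10, and 30×0.18 + 21×0.20 = 9.60. The rule removes only about 0.3 to 0.6 of a responder. The scarcity comes from low rates and small cohorts.

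**No responder in either cohort.** This happens only if both cohorts stop, so the chance is the product of the two values of S:

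- 5%: 0.95^27 = 0.25
- 10%: 0.90^27 = 0.06
- 18%/20%: 0.82^15 × 0.80^12 = 0.051 × 0.069 = 0.004

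**Information kept by a yes/no split.** Assume size change is normal and response is one cut of it. The squared correlation between the variable and its own split is φ(z)² / [p(1−p)], with z the cut that gives rate p.

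| True rate | Expected responders | P(no responder, both cohorts) | Information kept |
|---|---|---|---|
| 5% | 1.96 | 0.25 | 0.22 |
| 10% | 4.54 | 0.06 | 0.34 |
| 18%/20% (pooled 9.6/51 = 18.8%) | 9.34 | 0.004 | 0.48 |

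**Extra comparisons.** Three stains (c-kit, tryptase, chymase), serum tryptase and CgA make five markers. One added outcome means five more tests at 0.05. If these were independent, the chance of at least one false flag among them would be 1 − 0.95^5 = 0.23. A second added outcome tested formally would make ten: 1 − 0.95^10 = 0.40.

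**The case against.** Nothing here is an error. The plan admits that these analyses are underpowered, section 6.3.2 promises only description for tissue, and the open wording in section 8.2 does not bar percentage change. PFS is named for tissue and CgA, does not depend on the number of responders, and survives a cohort with none. All of this stands, and it is why the point is low priority. It does not remove the gap: PFS does not measure shrinkage, and tryptase change is tied by name to response alone.

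Three stronger readings are tempting and are not supported.

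- **A reader might infer that the response comparison usually fails when the drug is inactive**, because the chance that at least one cohort stops with no responder is 0.75 at a 5% rate. The plan does not say that marker analyses are run separately by cohort. Pooled, the comparison is impossible only when both cohorts have none, with a chance of 0.25.
- **A reader might infer that a continuous outcome is always more powerful.** Any power figure needs a marker–shrinkage correlation that the documents do not give. A model in which response is a cut of the same normal variable favours the continuous outcome by construction. If a marker differs only in full responders, the ranking reverses.
- **A reader might infer that missing 3-month CgA values bias the comparison with PFS.** Section 8.2 defines early CgA response by two measurements. Section 6.2 and Table 6-5 schedule CgA with the 3-cycle scan and at the end of treatment. Nothing counts an unmeasured patient as a non-responder.

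**Conclusion.** The point holds as a low-priority improvement to exploratory analyses. The primary test and the sample size are untouched. Confirmed response is the only named shrinkage outcome, few responders are expected unless the drug reaches its design rates, and a graded measure is already in the data.

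The expected counts and the zero-responder probabilities are exact under the stated design, given the true rate. The 22%, 34% and 48% rest on a normal size change and on response being a single cut of it. Confirmed response also depends on the repeat scan, non-target disease and new lesions, so these figures show the order of the loss rather than measure it.

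The gain is also limited to patients with a baseline and a post-baseline measurement and an available marker. Archival tissue is optional, and the CgA analysis covers only patients whose level is elevated.

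**What to change.** In sections 8.2 and 6.3.2:

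1. Add percentage change from baseline in the target-lesion sum at the first 12-week scan as a continuous exploratory outcome for the tissue, tryptase and CgA analyses. Analyse it by ranks, stratified by cohort. Keep responder yes/no and PFS beside it.
2. Show best percentage change only as a supportive description. It depends on how many scans a patient has, so a marker related to time on study could appear related to shrinkage.
3. State how patients with no post-baseline scan, new lesions or non-target progression are handled, and report how many there are. The choice is not neutral: under section 8.4, patients lost before the first scan are replaced unless the cause was toxicity or progression, so those who remain unscanned are a selected group. Section 5.4 continues regular tumour assessment after stopping for toxicity, while Table 6-5 footnote b leaves it off trial at the physician's discretion. These passages must be reconciled before the set with a 12-week value is defined.
4. Report the total number of comparisons and treat all results as descriptive.

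The cost is analysis wording only, with no new scans, visits or samples. There are two downsides: more tests under the unadjusted 0.05 flag, and lower power than yes/no if a marker matters only for full response. The second is the reason to add this outcome rather than substitute it.

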8.3 Sample-size Calculation

This will be a standard, phase II study, in which two cohorts of patients (carcinoid and pNET) consisting of 30 patients with carcinoid tumors and 21 patients with pNET each will be enrolled.

We have designed the study to test the null hypothesis that ibrutinib has a response rate of 5% or less in this disease. The sample size calculation has been based on the assumption that a true response of greater than 18% (comparable with that seen with agents such as sunitinib in pNET¹³ or bevacizumab in carcinoid tumors³¹) would generate interest in a larger randomized study. Taking into account both study feasibility given these relatively rare tumor and the relatively small difference in H1 and H0, with 30 patients in the carcinoid cohort we will be able to test the hypothesis that the true response is 18% versus 5% with a power of 80% and a type 1 error of 6%, while with 21 patients in the pNET cohort we will be able to test the hypothesis that the true response is 20% versus 5% with a power of 80% and a type 1 error of 8%. Patients will be accrued to the protocol according to a Simon's two-stage minimax design. In the carcinoid cohort, 15 subjects will be enrolled into stage-1. If 1 or more response is observed, then another 15 subjects will be enrolled into stage-2. At the completion of the study, if 4 or more responses out of N=30 are observed, significance at 6% is reached. Under this design, and if the true response rate is ≥18%, then the probability of observing ≥1 response in stage-1 is ≥95%. In the pNET cohort, 12 subjects will be enrolled into stage-1. If 1 or more response is observed, another 9 subjects will be enrolled into stage-2. At the completion of the study, if 3 or more responses out of N=21 are observed, significance at 8% is reached. Under this model, and if the true response rate is ≥20%, the probability of observing ≥1 response in stage-1 is 93%. In both cohorts, at least 1 patient must respond in the first stage to proceed to the second stage. At any point when it is realized that this cannot happen, the study will be stopped in the relative cohort, where the therapy will be considered ineffective.

Kaplan-Meier survival analysis will be performed to evaluate OS, PFS and duration of response.

8.4 Replacement of Dropouts

Patients who enroll but do not receive the initial dose of ibrutinib will be considered dropouts and may be replaced. Additionally, patients who drop out before the first scheduled follow-up scan (e.g. completion of the first four cycles of therapy) will be replaced, unless patients drop out due to dose-limiting toxicity or progressive disease. Assuming a 10% drop-out rate, 56 patients will need to be enrolled to reach 51 evaluable patients.

9. Safety Assessments

Safety assessments will consist of monitoring and recording all adverse events and serious adverse events, the regular monitoring of hematology and blood chemistry parameters, and regular physical examinations. These assessments should be performed within ±2 days of the scheduled day of assessment except for adverse events that will be evaluated continuously through the study. Safety and tolerability will be assessed according to the NIH/NCI CTC version 4.0. Please refer to:

http://ctep.cancer.gov/protocolDevelopment/electronic_applications/ctc.htm

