4.3 Study population

The study population will consist of adult patients with histologically confirmed low to intermediate grade NETs of the GI tract, lungs and unknown primary (carcinoid tumors) or pNETs. All patients must be confirmed to have advanced disease. The study will enroll up to 51 patients in two cohorts (30 carcinoid and 21 pNET patients).

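### Section 8.4 replaces some treated, unscanned patients without defining evaluable or planning an all-treated response rate, and its scan timing and enrolment total conflict with other sections

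*Combined protocol and SAP*

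**What the plan says.** Section 8.4 deals with two kinds of dropout.

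- Never dosed: "Patients who enroll but do not receive the initial dose of ibrutinib will be considered dropouts and may be replaced".
- Dosed but not yet scanned: "patients who drop out before the first scheduled follow-up scan (e.g. completion of the first four cycles of therapy) will be replaced". Two reasons for leaving are exempted from this rule: "unless patients drop out due to dose-limiting toxicity or progressive disease".

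The first kind is optional and the second is mandatory. The same section then gives the enrolment target: "Assuming a 10% drop-out rate, 56 patients will need to be enrolled to reach 51 evaluable patients".

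Other sections bear on this.

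- **Section 8.3** tests "the null hypothesis that ibrutinib has a response rate of 5% or less in this disease" with a two-stage rule per cohort: "In the carcinoid cohort, 15 subjects will be enrolled into stage-1" and "In the pNET cohort, 12 subjects will be enrolled into stage-1". Each cohort continues on at least 1 response. The final cut-offs are at least 4 of 30 and at least 3 of 21.
- **Section 4.3** says: "The study will enroll up to 51 patients in two cohorts (30 carcinoid and 21 pNET patients".
- **Sections 5.1 and 6.2 and Table 6-5 (column heading and footnote h)** put response scans every three cycles, so the first falls at 12 weeks.
- **Section 5.4** lists patient choice, investigator discretion and more than three weeks off treatment among the reasons for removal.
- **Section 7.1.5** says when a patient is not evaluable at one time point. It does not say who is evaluable for the primary analysis.

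**The concern.** The decisions rest on very small counts: one response in 15 or 12 to continue, then four in 30 or three in 21. Which patients fill those places can settle the result.

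The exceptions in Section 8.4 keep in the count the exits most closely tied to non-response. Patients who leave early by their own choice or by investigator decision are replaced. It is plausible, though the documents do not show it, that they would have responded less often than those who stay. The toxicity exception is also unclear. The term dose-limiting toxicity occurs only in Section 8.4, while other sections speak of unacceptable or intolerable toxicity. So it is open whether removal after more than three weeks off treatment, following a toxicity hold, counts as an exception. In an open-label single-arm trial these reasons are assigned with treatment and course known.

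At stake is whether the reported response rate, set against 5%, describes everyone treated or a selected subset. No planned analysis would show the difference.

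**Working it through.** **Inputs.** Section 8.3: null 5%; alternatives 18% (carcinoid) and 20% (pNET); stage sizes 15 + 15 and 12 + 9; continue on at least 1; cut-offs 4/30 and 3/21. Section 8.4: 10% dropout. Two inputs are assumptions: *d*, the share of treated patients replaced, and *f*, their response rate relative to the rate in all treated patients.

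**Step 1: reproduce the plan.** With first-stage size n1, total n, cut-off r and response rate p,

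P(success) = Σ over x ≥ 1 of P(X1 = x) × P(X2 ≥ r − x), where X1 ~ Bin(n1, p) and X2 ~ Bin(n − n1, p).

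At p = 0.05:

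- Carcinoid: 0.3658 × 0.0362 + 0.1348 × 0.1710 + 0.0307 × 0.5367 + 0.0055 = 0.058. The last term is P(X1 ≥ 4).
- pNET: 0.3413 × 0.0712 + 0.0988 × 0.3698 + 0.0196 = 0.080. The last term is P(X1 ≥ 3).

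Power is 0.800 at 18% and 0.803 at 20%. The stated 6%, 8% and 80% are confirmed.

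**Step 2: effect of replacement.** If p is the rate in all treated patients and replaced patients leave the denominator, then p = (1 − d)q + d·f·p. The rate among those kept is therefore q = p(1 − d·f)/(1 − d). With k patients replaced per cohort, d = k/(30 + k) or k/(21 + k). Example: k = 1, f = 0, carcinoid gives q = 0.05 × 31/30 = 0.0517. Putting q into Step 1 gives:

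| Replaced treated patients | f | Type 1 error, carcinoid | Type 1 error, pNET |
|---|---|---|---|
| None | – | 5.8% | 8.0% |
| 1 per cohort | 0.5 | 6.1% | 8.5% |
| 1 per cohort | 0 | 6.4% | 9.0% |
| 2 per cohort | 0.5 | 6.4% | 9.0% |
| 2 per cohort | 0 | 7.0% | 9.9% |
| 10% | 0.5 | 6.8% | 9.1% |
| 10% | 0 | 7.9% | 10.3% |
| Any share | 1 | 5.8% | 8.0% |

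The row with 10% and f = 0 is a ceiling at the plan's dropout rate. It treats every dropout as dosed, replaced and certain not to respond, whereas Section 8.4 counts never-dosed patients among its dropouts and gives no split. In that row the response rate is inflated by a factor of 1/0.9 = 1.11. The chance of passing stage 1 under the null rises from 53.7% to 57.6% (carcinoid) and from 46.0% to 49.6% (pNET).

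**Step 3: enrolment.** 56 × 0.9 = 50.4, which is below 51. If 10% of enrolled patients drop out, 51/0.9 = 56.7, so 57 are needed. Rounding up by cohort, 30/0.9 = 33.3 (34) and 21/0.9 = 23.3 (24), which makes 58. The plan's figure matches 51 × 1.1 = 56.1.

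**Step 4: scan timing.** Section 8.4 illustrates the first follow-up scan by completion of four cycles; the schedule has it after three. A patient leaving during cycle 4 would normally have been scanned already. By the operative words that patient is not replaced; by the example the patient would be.

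**The case against.** The strongest reply is that the denominator is largely implied. The rules use 30 and 21, which sum to 51, and Section 8.4 calls 51 the number of evaluable patients. The natural reading is that 56 enter, dropouts are replaced and 51 are analysed. If the 5% null is also meant for evaluable patients, the planned error rates hold. The only hint of an all-treated null is the reference to the disease, which names a tumour type and not an analysis set. This largely stands. A reader might infer that the trial has no denominator at all, or that its type 1 error is inflated as written; the documents support neither. What remains is that evaluable has no patient-level definition and that Sections 4.3 and 8.3 use enrolment language for the same 51.

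Second, the exceptions limit any bias. Section 5.4 lists symptomatic tumour progression beside documented progression, so such exits can fairly be read as excepted, and f = 0 is severe for the others. This stands too, and it is why the 10% figures are a ceiling.

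Third, the four-cycle text is only an example, and 56 against 57 is a rounding matter that changes no decision rule. Both are fair as to consequence, but both texts still need correcting.

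**Conclusion.** The point holds as a definitional gap with a small, conditional effect. Upward bias needs three things together: replaced patients leave the denominator, they respond less often than those kept, and the 5% null refers to all treated patients. Type 1 error (carcinoid / pNET) is then 6.1–6.4% / 8.5–9.0% with one replaced patient per cohort, for f between 0.5 and 0, and at most 7.9% / 10.3% at 10%. If dropout is unrelated to response, or the null refers to evaluable patients, there is no inflation. The share replaced and the response rate of replaced patients are assumptions; the documents give only the overall 10%.

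The undefined terms, the three- versus four-cycle conflict and the 51 versus 56 conflict need no assumption. A reader might also conclude that treated patients must never be replaced. The documents do not support that: it is a design choice that can be kept if the set and the null are defined to match. Severity: minor to moderate.

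**What to change.** 1. Reconcile the four-cycle example in Section 8.4 with the three-cycle schedule, and state that no patient with a post-baseline scan is replaced.
2. State that the two-stage rules and the 5% null apply to evaluable patients. Define evaluable at patient level, and define the toxicity exception used for replacement. Report the response rate in all treated patients beside the primary result, counting those with no post-baseline assessment as non-responders.
3. Reconcile 51 enrolled (Sections 4.3 and 8.3) with 56 (Section 8.4). If 10% of enrolled patients is meant, correct 56 to at least 57, or 58 if rounded up by cohort.

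Items 1 and 3 are wording, apart from one or two more planned enrolments if 56 is corrected. Item 2 adds one table and leaves the design unchanged.

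An option, not a required change, is to replace only never-dosed patients and score unassessed treated patients as non-responders within 30 and 21. If 18% and 20% were meant among scanned patients, power at p1(1 − d) falls from 80% to 78% / 77% with one unassessed patient per cohort (d = 1/30, 1/21), 75% / 74% with two, and 72% / 74% at 10%. If they were meant for all treated patients, power stays at 80%.
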